9.5 Week 8 Visit (Visit 4)

Participants will return to the study center at the end of Week 8 \pm 4 days (Visit 4) of the study. The evaluation at this visit will be the same as that completed at Week 4 (Visit 3).

9.6 Week 12 Visit (Visit 5)

Participants will return to the study center at the end of Week 12 \pm 4 days (Visit 5) of the study. In addition to the evaluations conducted at Week 8, the following will also be assessed:

- Psychiatric or quality of life evaluations:
 - CGI-S (Treating clinician)
 - CGI-I (Treating clinician)
 - CGI-EI (Treating clinician)
 - EQ-5D-5L
 - SF-36
 - Morisky scale (med compliance)
 - BARS scale (med compliance)

9.7 Long-Term Follow-Up - Months 6, 9 and 12 Visits (Visits 6, 7 and 8)

The long-term follow-up visits at the end of months 6 and 9 \pm 14 days (Visits 6 and 7) will be completed by telephone. The following will be evaluated at these visits:

- Psychiatric or quality of life evaluations:
 - HAM-D₁₇

- EQ-5D-5L
- SF-36 (only at month 6)
- Morisky scale (med compliance)
- BARS scale (med compliance)
- Current psychotropic medication and psychotropic medication trials since last visit
- Current concomitant non-psychotropic medications (including nicotine replacement and smoking cessation medications)
- Health resource utilization and productivity losses
- Documentation of disclosure of GEN report to participant at month 12 visit
- Participants will return to the study center at the end of month 12 (Visit 8) \pm 21 days of the study. The following will be evaluated at this visit:
- Psychiatric or quality of life evaluations:
 - QIDS-SR₁₆
 - HAM-D₁₇ (Central rater)
 - CGI-S (Treating clinician)
 - CGI-I (Treating clinician)
 - CGI-EI (Treating clinician)
 - PHQ-9
 - GAD-7
 - EQ-5D-5L
 - SF-36
- Smoking status and amounts
- Weight and waist-to-hip ratio
- Current psychotropic medication and psychotropic medication trials since last visit
- Current concomitant non-psychotropic medications (including nicotine replacement and smoking cessation medications)
- UKU side effect rating scale
- FIBSER
- AEs

- Medication adjustments (including dose changes, switching, augmentation and discontinuation)
- Medication compliance
- Health resource utilization and productivity losses

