9.2 Enrollment and Randomization

Patients who meet all the inclusion/exclusion criteria will be enrolled in the study with a 1:1:1 randomization allocation to one of three groups: GEN, E-GEN, or TAU. Investigators will be then given the results of the GEN test for the participants randomized to GEN, and of the E-GEN test for the participants randomized to E-GEN. Investigators will use the report to support their treatment decision based on this information. However, raters and participants will be blinded.

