9.3 Baseline Visit (Visit 2)

Within 14 days of Screening Visit, the baseline assessment visit for the study will be completed.

Prior to any change or adjustment in antidepressant medication, the following will be evaluated and recorded:

- Psychiatric or quality of life evaluations:
 - QIDS-SR₁₆
 - HAM-D₁₇ (Central rater)
 - CGI-S (Treating clinician)
 - PHQ-9
 - GAD-7
 - EQ-5D-5L
 - SF-36
- Patient demographics;
Patients' date of birth, age, gender, ethnicity, height (without shoes), annual income, highest education, and health insurance coverage will be recorded.
- Medical and psychiatric history;
- The complete medical history will be conducted with a review of all body systems and the patient's past and concurrent illnesses, drug use (including urine drug test), alcohol use, drug allergies, and family medical history. Particular attention will be paid to past psychiatric history, in particular age at first depressive episode, frequency of relapses, response to previous treatments, and other concomitant psychiatric disorders and their treatment.

- Past and current psychotropic medications including response; The generic name of the psychotropic medication, the doses used, start and end date, as well as response to treatment (efficacy and AEs) will be recorded.
- Past (within three months) and current concomitant non-psychotropic medications (including nicotine replacement and smoking cessation medications); The generic name of the medication, the doses used, start and end date will be recorded.
- Smoking status and amounts
- Weight (without shoes, with clothes) and waist-to-hip ratio
- Changes (if any) to physician's prescription of psychotropic medication based on availability of pharmacogenomics data in GEN and E-GEN
- PIP-FQ
- UKU side effect rating scale
- FIBSER
- AEs
- Medication adjustments (including dose changes, switching, augmentation and discontinuation)
- Health resource utilization and productivity losses

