13.0 BLINDING

This study will be conducted under double-blind conditions so that neither the patient nor study staff members involved in patient assessments will know whether the patient is receiving GEN, E-GEN, or TAU. Only the treating clinician at the study site and AssureRx will have knowledge of the intervention arm assigned to the patient.

All assessments will be administered by the site, with the exception of the primary outcome measure (HAM-D₁₇), which will be conducted by 1-2 trained central rater(s) not involved in the clinical care of the individual and blinded to the treatment allocation. The rater will be trained and inter-rater reliability will be determined through rater scoring of the HAM-D₁₇ while viewing a DVD-recording of a standardized patient interview.

At randomization, the treating clinician will receive the results of the GEN test for patients allocated to GEN and the results of the E-GEN test for patients allocated to the E-GEN, and may decide to change the participant's treatment based on the results of the test. The treating clinician will therefore not be blinded to treatment allocation. AssureRx will also not be blinded to treatment allocation in order to release the appropriate report (either GEN, E-GEN or no report (TAU)) to the treating clinician and to provide follow-up support to the treating clinician on report interpretation. However, both treating clinician and AssureRx will be blinded to trial data.

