3. EFFICACY INDEX (CGI-EI)

Rate this item on the basis of DRUG EFFECT ONLY Select the terms which best describe the degrees of therapeutic effect and side effects and record the number in the box where the two items intersect.

EXAMPLE: Therapeutic effect is rated as "Moderate" and side effects are judged "Do not significantly interfere with patient's functioning." Record 06

THERAPEUTIC EFFECT	SIDE EFFECTS			
	None	Does not significantly interfere with patient's	Significantly interfere with patient's functioning	Outweigh therapeutic effect

		functionin g		
MARKED – Vast improvement. Complete or nearly complete remission of all symptoms	01	02	03	04
MODERATE – Decided improvement. Partial remission of symptoms	05	06	07	08
MINIMAL – Slight improvement which doesn't alter status of care of patient	09	10	11	12
UNCHANGED OR WORSE	13	14	15	16

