#### **3.2 Analysis Populations**

##### **3.2.1 Per Protocol (PP) Population**

The primary statistical analysis will be performed using the Per Protocol (PP) principle. The population of this analysis will be all subjects who met the inclusion and exclusion criteria. Other variables relating to exclusion may include but are not limited to:

At screening:

- a) Meets all inclusion/exclusion criteria (except exception 8 and 13)
- b) All assessments completed by appropriate person
- c) QIDS-C16 and -SR16 are  $\geq 11$

At baseline:

- a) Confirmation that subject still satisfies all Inclusion/Exclusion criteria
- b) Randomization occurred prior to the Baseline visit

- c) All assessments completed by appropriate person. The Blinded Rater should administer the QIDS-C16, not the Treating Clinician.
- d) Baseline was completed within 42 days of screening
- e) Sample was received and report was released (GEN & E-GEN) prior to baseline
- f) Report was viewed (GEN & E-GEN) at/prior to baseline
  - o If report not viewed at/prior to baseline, prescription decision date must follow view date of report
- g) Baseline QIDS-SR is  $\geq 11$
- h) Baseline HAM-D-17  $\geq 14$

After enrollment:

- a) Week 4 visit occurs within 20-36 days of baseline visit
- b) Week 8 visit occurs within 48-64 days of baseline visit
- c) QIDS-C16 completed by Blinded Rater, not Treating Clinician
- d) Subject did not start ECT, DBS, or TMS
- e) MDD Rx given by study affiliated clinician
- f) If unblinding occurs before week 8 visit, data is not included in PP population

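### CGI-S, CGI-I and CGI-EI are rated by the unblinded treating clinician, contrary to the protocol's blinded-rater rule, and the SAP tests them between arms without a caveat

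*Protocol*

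**What the plan says.** **Blinding rule.** Protocol 13.0 states that "neither the patient nor study staff members involved in patient assessments will know whether the patient is receiving GEN, E-GEN, or TAU". Section 9.2 adds: "However, raters and participants will be blinded". Section 5.0 also extends the double blind to participants and raters.

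**Treating clinician.** The same section 13.0 says: "The treating clinician will therefore not be blinded to treatment allocation". In GEN and E-GEN this clinician receives the report and is free to act on it or not.

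**Who rates the CGI.** Section 9.3 (baseline) lists "CGI-S (Treating clinician". Section 9.6 (Week 12) lists CGI-S, "CGI-I (Treating clinician" and "CGI-EI (Treating clinician", and 9.7 repeats the three for Month 12. Section 9.8 makes the Early Termination visit a repeat of Week 12, and Figure 1 marks all three CGI items there. Only the HAM-D17 goes to a blinded central rater.

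**How the CGI is used.** Protocol 1.4 and 8.2.1 place the three measures among the secondary outcomes; SAP 2.1.4 and 2.2.3 place them among the exploratory, safety and tolerability ones. SAP 5.2 analyses CGI-S percentage change with the primary-endpoint method, and CGI-S, CGI-I and CGI-EI response (and CGI-S remission) with the same mixed model used for HAM-D17 response.

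**Rater checks.** SAP 3.2.1 has a rater-identity condition for another scale: "The Blinded Rater should administer the QIDS-C16, not the Treating Clinician". None names the CGI.

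**The concern.** One person is both an outcome rater and aware of the arm, which the blinding rule excludes. The statements cannot all be true as written.

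The CGI is also a scale on which expectation can easily act. CGI-I is a global judgement of improvement. The CGI-EI form instructs: "Rate this item on the basis of DRUG EFFECT ONLY", and the person giving that rating prescribes the drug and, in two arms, holds the report under test. The SAP 7.1 thresholds are narrow: a one-point fall counts as CGI-S response, and a CGI-I score of 3 (minimally improved) counts as response, so a shift of one category can change a patient's status.

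At stake is how these results are read. SAP 1.1 says the findings are meant to inform guidelines and will go to a provincial health technology application. There, a clinician-rated global improvement from a trial described as double-blind could pass as blinded corroboration.

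**Working it through.** **1. The passages side by side**

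| Question | Where | Content |
|---|---|---|
| Do assessors know the arm? | Protocol 5.0, 9.2, 13.0 | No |
| Does the treating clinician know the arm? | Protocol 13.0 | Yes |
| Who rates CGI-S at baseline? | Protocol 9.3 | Treating clinician |
| Who rates CGI-S, CGI-I, CGI-EI at Week 12 and Month 12? | Protocol 9.6, 9.7 | Treating clinician |
| And at Early Termination? | Protocol 9.8 | As Week 12 |
| Who rates HAM-D17? | Protocol 13.0 | Blinded central rater |
| Is any CGI collected at Week 8? | Protocol 9.5, Figure 1 | No |
| Is the CGI tested between arms? | SAP 5.2 | Yes, without a caveat |

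Rows 2 to 5 contradict row 1 for every CGI rating in the trial. Rows 6 and 7 confine the problem to the CGI.

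The baseline CGI-S is included. Randomization precedes the baseline visit (Protocol 9.1 and 9.2), so the clinician can know the arm when giving the score from which change is measured.

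**2. Illustration of sensitivity**

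The plan has no figure to reproduce, and the documents give no size for rater bias. The shifts below are assumptions, in favour of the tested arm and with no true effect.

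- Inputs: 190 per arm and 16.7% discontinuation by Week 8 (Protocol 10.0); two-sided 0.05 (SAP 6).
- Evaluable per arm: 190 × (1 − 0.167) = 158.27, taken as 158. The CGI is collected at Week 12 and later, so the true number may be lower.
- Standard error in SD units: one arm against TAU, √(1/158 + 1/158) = 0.1125. GEN and E-GEN pooled against TAU, as SAP 2.1.2.2 allows, √(1/316 + 1/158) = 0.0974.
- Probability of a significant result with rater shift b: 1 − Φ(1.96 − b/SE) + Φ(−1.96 − b/SE).
- Example, b = 0.10, 1:1: 0.10/0.1125 = 0.889, so 1 − Φ(1.071) + Φ(−2.849) = 0.142 + 0.002 = 0.144.

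| Assumed shift (SD) | 158 v 158 | Pooled 316 v 158 |
|---|---|---|
| 0 | 5.0% | 5.0% |
| 0.05 | 7.3% | 8.1% |
| 0.10 | 14.4% | 17.7% |
| 0.20 | 42.8% | 53.7% |
| 0.30 | 76.0% | 86.8% |

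For a responder endpoint, assume a 50% rate. A 5-point shift has standard error √[(0.50 × 0.50 + 0.55 × 0.45)/158] = 0.0561, and 0.05/0.0561 = 0.891, so the chance of significance is 1 − Φ(1.069), about 14% (about 18% pooled). A 10-point shift gives about 43% (54% pooled).

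**The case against.** **The protocol discloses the facts.** The rater is printed beside each CGI item, and 13.0 says that clinician is unblinded. This stands in part: a reader who joins the two sections can see the CGI is unblinded, so it would be wrong to say the documents hide it. What is missing is an exception in 13.0 and a caveat in the SAP.

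**The endpoints rank low.** The SAP supersedes the protocol's analysis plan and makes the CGI exploratory. The CGI is in none of the primary, ordered secondary or long-term secondary objectives. This stands and limits the weight of the point. A reader might infer that the HAM-D17 conclusion is compromised; the documents do not support that, because the primary comparison is at Week 8, is centrally and blindly rated, and has no CGI beside it.

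**Bias is not shown.** A reader might infer that the CGI is biased toward the tested product. Nothing in the documents establishes direction or size, and the calculation starts from assumed shifts. It shows how sensitive the tests would be, not that a shift occurred. Open to bias is as far as the text goes.

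**The report may not have shaped the rating.** A reader might infer that the clinician chose the drugs from the report, or had read it before the baseline CGI-S. Protocol 7.1.1 and 7.1.2 make use optional. SAP 3.2.1 accepts a report viewed after baseline if prescribing follows the viewing. TAU clinicians have no report until up to 28 days before 12-month completion. The objection stands on use of the report; it does not remove knowledge of the arm, which 13.0 grants the treating clinician in every arm.

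**Conclusion.** The contradiction is real. For CGI-S, CGI-I and CGI-EI, at every visit where they are collected including Early Termination, blinded rating is a stated property that the design does not have. The SAP then tests these ratings between arms on the same footing as blinded scales.

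A between-arm CGI difference could reflect treatment, rater expectation or both, and nothing collected would separate them. Under the assumptions shown (158 per arm, no true effect, shift favouring the tested arm), a shift of 0.10 SD would nearly triple the nominal 5% error, to 14.4%, and 0.20 SD would take it to 42.8%. The actual shift is unknown and may be nil.

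This should be corrected in the text and in reporting. It does not affect the validity of the primary analysis.

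**What to change.** **1. For all participants: state and label.** Amend Protocol 13.0 to say that CGI ratings by the treating clinician are an exception to rater blinding. In SAP 2.1.4 and 5.2, label CGI-S, CGI-I and CGI-EI as unblinded and report them descriptively by arm, without a between-arm efficacy test. The cost is a few sentences and the loss of exploratory tests that could not be interpreted with confidence.

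**2. Optional, for participants not yet at baseline: a blinded rating.** The central rater can score CGI-S and CGI-I at the existing HAM-D17 assessment. Change the rater in 9.3, 9.6 and 9.7 (9.8 follows by reference), and list these two items with HAM-D17 in 13.0 as centrally rated, since that section now leaves every other assessment to the site. If CGI-EI stays with the treating clinician, item 1 continues to apply to it. The site Blinded Rater in SAP 3.2.1 is a less ready substitute: that role is named only for QIDS-C16, which Figure 1 schedules only at screening.

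Do not change rater within a participant, because CGI-S change would then compare two raters' scores.

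Item 2 needs no new staff, only a short addition to an existing interview. Its drawbacks are that the central rater knows the patient less well, and that ratings already collected by treating clinicians stay flagged as unblinded.

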9.8 Early Termination (ET) Visit

If ET occurs, the participant should attend an in-clinic visit as soon as possible to complete ET procedures that will consist of all procedures scheduled for Week 12 (refer to section on Week 12 Visit (Visit 5)).

9.9 Unscheduled Visits

Investigators may see participants for clinical management of their depression at any time. There is no “Unscheduled Visit” in this study but the visit should be recorded in the patient chart as per standard clinical practice.

10.0 SAMPLE SIZE

The study will recruit participants from approximately 8-12 sites stratified into 2 clusters. CAMH will constitute one study site and a single stratified cluster. The remaining sites will constitute the second cluster. The sample size required for this study was calculated using effect size estimates drawn from a previous study conducted by Hall-Flavin et al.(11) Assuming an effect size of 0.30 in HAM-D₁₇ score favoring the treatment group, intra class coefficient between clusters of 20%, statistical power of 90%, an alpha level of 0.05, and an expected 16.7% rate of premature discontinuation (based on ongoing studies and experience with the intervention) by Week 8 (primary endpoint), a total of 570 participants (i.e., 190 per treatment arm) are required to detect the same effect in this study. Sample size calculations were determined using SAS (SAS Institute, Inc., Version 9.3, Cary, NC).

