4.2 Primary Objectives

The first primary objective of this study is to compare the efficacy of GEN to TAU in improving response to psychotropic treatment in outpatients suffering from a major depressive disorder (MDD) and having had – within the current episode - an inadequate response to at least one psychotropic medication included in GEN.

The second primary objective for this study is to validate the utility of the new CAMH markers and demonstrate the superior predictive capabilities and greater clinical utility of E-GEN as compared to GEN.

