16.1.2 Diagnostics

Prior to formal statistical analyses, diagnostics will be conducted to determine appropriate statistical models. The independence assumption of ANOVA will be tested by examining the correlation between error terms for each dependent variable across levels of the indicator variable. To this end, the Durbin-Watson test statistic will be used to determine if the independence assumption was upheld. Values approaching 2.0 from the left or right were considered to be an indication of independence. The normality assumption will be tested by plotting residuals against the normal probability plot and by deriving the Shapiro-Wilk (S-W) test statistic. The dependent variable will formally be considered to be non-

normally distributed if the p-value for the S-W test was < 0.05 . Homogeneity of variance will be tested by employing the statistic derived by Brown and Forsythe. If the associated p-value for the test statistic is < 0.05 , then the dependent variable will be assumed to exhibit non-constant variance. If a given dependent variable did not meet the above mentioned assumptions (e.g., clustering due to study site), generalized estimating equations (GEEs) will be employed to account for the lack of independence between outcomes using an autoregressive correlation structure and identity link function.

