16.1.3 Continuous Outcomes

If the HAM-D₁₇ scores from baseline to end of Week 8 of the study meet the assumptions of ANOVA modeling, repeated-measure (i.e., mixed) ANOVA models will be used to model the outcome scores over time. This model accounts for a between-group and within-individual effect, which allows for the examination of average differences between groups while also accounting for the correlation between participant scores between each measurement. If the HAM-D₁₇ scores do not meet standard ANOVA assumptions, GEEs will be used to model repeated measurements of outcome scores over time, as these models are more robust to departures from the standard assumptions and also allow the investigator to specify the correlation structure of the repeated measurements. Mean symptom improvement for all continuous measures (i.e., depression scales) will be calculated using the standard formula $(\frac{y_2 - y_1}{y_1}) * 100$, where y_1 is the baseline score for each participant for each rating scale and y_2 is the 8 week score for each participant for each rating scale.

Two hypotheses related to the primary objectives will be tested, where μ_1 is the mean HAM-D₁₇ % symptom improvement in the GEN group, μ_2 is the mean HAM-D₁₇ % symptom improvement in the E-GEN group and μ_3 is the mean HAM-D₁₇ % symptom improvement in the TAU group.

Primary objective (1):

$$H_0: \mu_1 = \mu_2 = \mu_3$$

$$H_a: \mu_1 = \mu_2 > \mu_3$$

Primary objective (2):

$$H_0: \mu_1 = \mu_2 = \mu_3$$

$$H_a: \mu_1 < \mu_2 > \mu_3$$

For all continuous measures, a responder will be defined as a participant with 50% change from baseline in total scale score. Remitters at week 8 and at week 12 will be defined as HAM-D₁₇ ≤7 in each treatment group. Differential time to response/remission of depressive symptoms over 8 and 12 weeks will be plotted using Kaplan-Meier curves and Cox proportional hazard models will test the null hypothesis of no difference in time to response/remission between groups.

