16.1.6 Decision Rule

An overall alpha-level of 0.05 will be used to determine statistical significance and all statistical tests will be two-sided. All data will be analyzed using SAS (SAS Institute, Inc., Version 9.3, Cary, NC).

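### The 90% power in protocol section 10.0 is not supported by its own inputs for the two-sided GEN versus TAU primary test: about 76%, or 84% with full credit for the ICC, before any covariate gain

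*Protocol*

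**What the plan says.** Protocol section 10.0 takes an effect size of 0.30 on the HAM-D17 from an earlier open-label study, "favoring the treatment group". It adds an "intra class coefficient between clusters of 20" percent (two clusters: one large site, and all the others) and "statistical power of 90%, an alpha level of 0.05, and an expected 16.7% rate of premature discontinuation" by Week 8. Its conclusion is that "a total of 570 participants (i.e., 190 per treatment arm) are required to detect the same effect in this study". The section does not say which arms are contrasted, whether the test is one- or two-sided, what scale the 0.30 is on, or how the intraclass coefficient (ICC) is used.

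The rest of the documents narrows this down:

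- Protocol 4.2: "The first primary objective of this study is to compare the efficacy of GEN to TAU in improving response to psychotropic treatment".
- Protocol 16.1.3: "Two hypotheses related to the primary objectives will be tested". The first alternative sets GEN and E-GEN equal and both better than TAU.
- Protocol 16.1.6: "all statistical tests will be two-sided". SAP section 6 also sets 0.05, two-sided.
- SAP 1.2 replaces the protocol's analysis plan. SAP 2.1.1 has a single primary hypothesis, GEN versus TAU on percentage change in HAM-D17 at Week 8. GEN versus E-GEN is secondary (SAP 2.1.2.2).
- SAP 5.1 fits an MMRM with treatment, week, baseline HAM-D17 and their interactions with week. It has no site or cluster term. The main conclusion comes from the per-protocol set (SAP 3.2.1 and 3.4).

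**The concern.** A reader will attach the 90% to the primary test, which is two-sided GEN versus TAU. A rough check shows that 190 per arm is too few for a standardised difference of 0.30 at 90% power, even before dropout is taken off.

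This matters most if the result is null. Readers would assume a 10% chance of having missed a true 0.30 effect, when the stated inputs allow a chance of up to about 24%. The SAP says the results are meant to inform guidelines and a health technology application, so the reading of a null result has consequences. The planned 95% intervals help with that reading but do not correct the stated power.

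**Working it through.** **Inputs.** From protocol 10.0: effect size d = 0.30, alpha 0.05, ICC 0.20, dropout 16.7%, N = 570. Two-sided testing is from protocol 16.1.6 and SAP 6; 1:1:1 allocation is from protocol 5.0. *Assumption:* 0.30 is a standardised mean difference (SD 1). Read instead as Cohen's f for three groups, 0.30 would need only about 48 evaluable per arm for 90%, so 570 does not fit that reading.

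**Evaluable patients.** 570 × (1 − 0.167) = 474.8; 474.8 / 3 = 158.3 per arm.

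**Role of the ICC.** Patients are randomised individually within site (protocol 12.1.1), so no cluster-randomisation penalty applies. The most favourable reading is that between-cluster variance is removed. The SD becomes √(1 − 0.20) and d becomes 0.30 / √0.80 = 0.335. I call this full ICC credit.

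**Power, normal approximation.** Power = Φ(d × √(n/2) − 1.960), with √(158.3/2) = 8.897.

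- No ICC credit: 0.30 × 8.897 − 1.960 = 0.709, Φ = 76.1%.
- Full ICC credit: 0.335 × 8.897 − 1.960 = 1.024, Φ = 84.7%.

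With the noncentral t and 158 per arm these become **75.8%** and **84.4%**. Removing 10% of the variance gives 80.0%.

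**Size needed for 90%.** n = 2(1.960 + 1.282)² × (1 − ICC) / d². This gives 233.5 per arm without ICC credit and 186.8 with it; by noncentral t, 235 and 188. Dividing by 0.833 gives about 283 and 226 randomised per arm, against 190. The difference detectable with 90% power at 158 per arm is about 0.37 without ICC credit and 0.33 with it.

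**Attempts to reproduce the 90%** (noncentral t or F):

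| Reading | Power | Where it departs from the documents |
|---|---|---|
| GEN vs TAU, two-sided, 158 per arm, no ICC credit | 75.8% | gives the ICC no role |
| GEN vs TAU, two-sided, 158 per arm, full ICC credit | 84.4% | none, but the SAP model has no term to earn the credit |
| GEN vs TAU, two-sided, 190 per arm, no ICC credit | 83.1% | ignores dropout |
| GEN vs TAU, two-sided, 190 per arm, full ICC credit | 90.3% | ignores dropout |
| GEN vs TAU, one-sided, 190 per arm, no ICC credit | 89.9% | ignores dropout; one-sided |
| GEN vs TAU, one-sided, 158 per arm, full ICC credit | 90.8% | one-sided |
| GEN + E-GEN (316) vs TAU (158), two-sided | 86.7% without, 93.0% with full ICC credit | not the SAP primary test |
| Pooled, one-sided, 316 vs 158, no ICC credit | 92.4% | one-sided; not the primary test |
| Pooled, two-sided, 380 vs 190, no ICC credit | 92.1% | ignores dropout; not the primary test |
| Three-group F test, f = 0.141, N = 475 | 79.1% without, 87.8% with full ICC credit | not the primary test |
| Three-group F test, f = 0.15, N = 570, no ICC credit | 90.2% | ignores dropout; f too large |
| Three-group F test, f = 0.15, N = 475, full ICC credit | 91.4% | f too large |

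On the last two rows: the largest f that a 0.30 range across three equal arms can give is 0.30 × √2 / 3 = 0.141.

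**Covariate gain.** The MMRM uses baseline HAM-D17 and Week 4 data, which the figures above do not. Reaching 90% needs 32.7% of the variance explained (correlation √0.327 = 0.57) without ICC credit, or a further 15.9% (0.40) on top of full ICC credit. The documents give no correlation. Over an assumed range for the baseline correlation:

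| Correlation | No ICC credit | Full ICC credit |
|---|---|---|
| 0.3 | 79.6% | 87.6% |
| 0.4 | 82.7% | 90.0% |
| 0.5 | 86.6% | 92.9% |
| 0.6 | 91.4% | 96.0% |

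**The case against.** The strongest reply is that section 10.0 is under-specified rather than miscalculated. Two readings keep its own inputs and pass 90%: the pooled two-sided contrast (93.0%) and a one-sided pairwise test (90.8%), both with full ICC credit. The section itself states no sidedness, its wording is directional, and so are the alternatives in protocol 16.1.3. It is also true that 76% is the power of a plain two-sample test. The planned MMRM should do better, and 0.30 comes from a study whose definition cannot be checked here.

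Part of this stands. The sponsor may have powered a different contrast, and the calculation does not show that the true power is below 90%. None of it supports 90% for the primary test. The one-sided route contradicts the two-sided rule in both documents. The pooled contrast is not the SAP's primary comparison; it enters only after the GEN versus E-GEN step. The covariate gain may be real, but section 10.0 claims none and nothing in the documents sizes it.

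**Conclusion.** The concern holds. For the two-sided GEN versus TAU test, the inputs in section 10.0 give 75.8% power without ICC credit and 84.4% with full credit, against the stated 90%. The corresponding chance of missing a true 0.30 effect is about 24% or 16%, against 10%.

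This rests on reading 0.30 as a standardised mean difference and on 158 evaluable per arm. At that size the figures are floors, because baseline and Week 4 data are not used. The per-protocol set on which the main conclusion rests may be smaller than 158 per arm, which would work the other way. The finding is that 90% is unsupported as written for this test, not that the trial's actual power must fall short.

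**What to change.** Rewrite section 10.0 and carry the result into the SAP, which has no power statement. The text should:

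- name the contrast, sidedness and test to which 90% applies;
- define the 0.30;
- state how the 20% ICC enters, and any gain assumed from baseline or Week 4 data;
- give the GEN versus TAU power at the stated dropout;
- note that the per-protocol set may be smaller than 158 per arm.

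Suggested wording:

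> If 0.30 is a standardised mean difference, 190 randomised and about 158 evaluable participants per arm give the two-sided 0.05 test of GEN versus TAU about 76% power without credit for the ICC and 84% with full credit, before any gain from baseline or Week 4 data. Power of 90% is reached at a difference of about 0.37 (0.33 with full ICC credit).

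If 90% was meant for GEN and E-GEN pooled against TAU, say so and give the pairwise figure beside it. Do not describe E-GEN versus GEN as having 90% power: section 10.0 makes no explicit claim for it and the SAP lists it as secondary.

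The cost is wording in two documents and a less favourable stated power. The correction itself needs no added patients; whether the restated power is acceptable is for the sponsor to decide.
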